#### Missing month only

- If only the month is missing, the day will be treated as missing and both the month and the day will be replaced according to the above procedure.

#### Missing day only

- If the month and year of the incomplete start date are the same as the month and year of the first dose of open-label IP, the day of the first dose of open-label IP will be assigned to the missing day.
- If either the year of the incomplete start date is before the year of the date of the first dose of open-label IP or if both years are the same, but the month of the incomplete start date is before the month of the date of the first dose of open-label IP, the last day of the month will be assigned to the missing day.
- If either the year of the incomplete start date is after the year of the date of the first dose of open-label IP or if both years are the same, but the month of the incomplete start date is after the month of the date of the first dose of open-label IP, the first day of the month will be assigned to the missing day.

### 15.8.2 Incomplete Stop Date

The following rules will be applied to impute the missing numeric fields for an incomplete prior or concomitant medication stop date. If the imputed stop date is before the start date (imputed or non-imputed start date), the imputed stop date will be equal to the start date.

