## **6.0**

### **DEMOGRAPHICS AND OTHER BASELINE CHARACTERISTICS**

Demographic parameters (eg, age, race, ethnicity, sex, weight, height, body mass index) and other baseline characteristics will be summarized overall for the Open-label ITT Population and by treatment group for the Double-blind mITT Population.

Medical and surgical history, psychiatric history, previous treatment with psychotropic medication, and nondrug psychiatric treatment will be summarized overall for the Open-label Safety Population and by treatment group for the Double-blind Safety Population.

Prior medication is defined as any medication started before the date of the first dose of open-label IP. Concomitant medication during the OLTP is defined as any medication taken on or after the date of the first dose of open-label IP during the OLTP. Concomitant medication during the DBTP is defined as any medication taken on or after the date of the first dose of double-blind IP during the DBTP.

The use of prior and concomitant medications during the OLTP will be summarized by the number and percentage of patients receiving each medication within each therapeutic class for the Open-label Safety Population. Concomitant medications during the DBTP will be summarized by treatment group by the number and percentage of patients receiving each medication within each therapeutic class for the Double-blind Safety Population. Multiple medication use of the same therapeutic class by a patient will only be counted once. Concomitant medications started after the patient's last study visit during their last treatment period will not be summarized but will be included in the data listings.

Prior ADT treatment in the current episode, as recorded on the ATRQ collected in the lead-in studies, will be summarized by frequency counts and percentages for patients who took each ADT in adequate dose and duration, total number of ADT taken at adequate dose and duration (ie, 1, 2, 3 or more), and percentage of improvement reported (ie, < 25%, 25% to 49%, 50% to 75%, or >75%). For the OLTP, the summaries will be overall for the Open-label Safety Population. For the DBTP, the summaries will be by treatment group for the Double-blind Safety Population.

The *WHO Drug Dictionary Enhanced* will be used to classify prior and concomitant medications by therapeutic class and drug name.

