## **7.0 EXTENT OF EXPOSURE AND TREATMENT COMPLIANCE**

### **7.1 EXTENT OF EXPOSURE**

Exposure to open-label rapastinel for the Open-label Safety Population during the OLTP will be summarized for treatment duration, calculated as the number of days from the date of the first dose of open-label rapastinel taken to the date of the last dose taken during the OLTP, inclusive. Descriptive statistics will be presented.

Exposure to double-blind IP for the Double-blind Safety Population during the DBTP will be summarized for treatment duration, calculated as the number of days from the date of the first dose of double-blind IP taken to the date of the last dose taken during the DBTP, inclusive. Descriptive statistics will be presented by treatment group.

The number of IV doses of rapastinel administered to each patient during the OLTP will be summarized using descriptive statistics for the Open-label Safety Population.

Similarly, the number of IV doses administered to each patient during the DBTP will be summarized by treatment group, using descriptive statistics for the Double-Blind Safety Population.

The number and percentage of patients taking each qualifying ADT in the OLTP will be summarized for the Open-label ITT Population; the number and percentage of patients taking each qualifying ADT in the DBTP will be summarized by double-blind treatment group for the Double-Blind mITT Population. Mean daily dose and duration of previous treatment with each qualifying ADT will be summarized using descriptive statistics for the OLTP and by double-blind treatment group for the DBTP for the respective ITT or mITT populations.

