## 15.8 MISSING DATE INFORMATION FOR PRIOR OR CONCOMITANT MEDICATIONS

For prior or concomitant medications, including background ADT, incomplete (ie, partially missing) start dates and/or stop dates will be imputed. When the start date and the stop date are both incomplete for a patient, the start date will be imputed first.

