### 15.8.1 Incomplete Start Date

The following rules will be applied to impute the missing numeric fields for an incomplete prior or concomitant medication start date. If the stop date is complete (or imputed) and the imputed start date is after the stop date, the start date will be imputed using the stop date.

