#### Missing month and day

- If the year of the incomplete start date is the same as the year of the first dose of open-label IP, the month and day of the first dose of open-label IP will be assigned to the missing fields.
- If the year of the incomplete start date is before the year of the first dose of open-label IP, 31 Dec will be assigned to the missing fields.
- If the year of the incomplete start date is after the year of the first dose of open-label IP, 01 Jan will be assigned to the missing fields.

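### SAP 15.8.1 and 15.8.2 correct out-of-order imputed medication dates in opposite directions, and the stated order can turn a drug stopped before open-label dosing into a concomitant one

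*SAP*

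**What the plan says.** SAP Section 15.8 sets the order: "When the start date and the stop date are both incomplete for a patient, the start date will be imputed first".

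Section 15.8.1 then gives an override for imputed starts, which applies whether the stop was recorded in full or was itself imputed: where "the imputed start date is after the stop date, the start date will be imputed using the stop date". Section 15.8.2 gives an override for imputed stops. If the imputed stop precedes the start, whether or not that start was itself imputed, then "the imputed stop date will be equal to the start date".

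The values that feed these overrides are:

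- A start with month and day missing, in the year of the first open-label dose: "the month and day of the first dose of open-label IP will be assigned to the missing fields" (15.8.1).
- A stop with only the day missing, in a month before that of the last dose: the last day of the recorded month (15.8.2).

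The classification is in Section 6.0: "Prior medication is defined as any medication started before the date of the first dose of open-label IP". A medication is concomitant in the open-label treatment period (OLTP) if it was taken on or after the first-dose date during that period.

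**The concern.** Both overrides, by their own wording, cover the case where both dates are imputed and out of order, and they move opposite dates. Under the order in 15.8, no imputed stop exists yet when the start is imputed, so 15.8.1's reference to an imputed stop has nothing to act on and 15.8.2 decides. The result can contradict the case report form: a stop whose month was recorded is carried forward past that month.

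At stake are the tables showing which other treatments patients had before and during open-label rapastinel. A misplaced record is wrong in both tables, because it leaves the prior summary and enters the OLTP concomitant summary.

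**Working it through.** The SAP gives no figure to reproduce, so the check applies the rules to dates. All calendar dates below are assumed for illustration.

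**Example 1: stop month recorded, start month not.** First open-label dose 15 Jun 2018; last dose 10 Jan 2019; start recorded as 2018; stop recorded as Mar 2018.

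1. Start (15.8.1, month and day missing, same year as first dose) = 15 Jun 2018.
2. Stop (15.8.2, day missing, before the last-dose month) = 31 Mar 2018.
3. The imputed start is after the imputed stop, so an override applies.

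| Override | Start | Stop | Prior? | Concomitant in OLTP? |
|---|---|---|---|---|
| 15.8.2 (acts under the 15.8 order) | 15 Jun 2018 | 15 Jun 2018 | No | Yes |
| 15.8.1 | 31 Mar 2018 | 31 Mar 2018 | Yes | No |

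The recorded stop month, March, agrees only with the second row.

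**Example 2: start month recorded, stop month not.** First open-label dose 15 Jun 2018; last dose 10 Aug 2018; last visit in mid-August; start recorded as Oct 2018; stop recorded as 2018.

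1. Start (day missing, after the first-dose month) = 1 Oct 2018.
2. Stop (month and day missing, same year as last dose) = 10 Aug 2018.
3. 15.8.2 sets the stop to 1 Oct 2018 and respects the recorded start month. The drug began after the last study visit, so Section 6.0 leaves it out of the summary.
4. 15.8.1 would set the start to 10 Aug 2018, overwrite October and make the drug concomitant.

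Each override is therefore right in one pattern and wrong in the other.

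**How far the clash reaches.** All pairs of partial dates with a known year were enumerated, from the year before first dose to the year after last dose, for three assumed pairs of dose dates.

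| First / last dose | Start year only, stop month known: clashes | of which class changes | Start month known, stop year only: clashes |
|---|---|---|---|
| 15 Jun 2018 / 10 Dec 2018 | 16 | 5 | 11 |
| 15 Jun 2018 / 10 May 2019 | 16 | 5 | 18 |
| 20 Sep 2017 / 1 Oct 2018 | 19 | 8 | 13 |

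- The class changes are the stop months before the first-dose month in the first-dose year: 6 − 1 = 5 for June and 9 − 1 = 8 for September.
- The other 11 (16 − 5, or 19 − 8) lie in the year before first dose. The start becomes 31 Dec, and a stop in any month from January to November is overwritten, but the drug stays prior.
- In the last column, neither override changes the comparison with the first-dose date.
- When both dates lack only the day, or both lack month and day, there is no clash.

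These are counts of possible date patterns, not of patients or records.

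**The case against.** The strongest reply is that the procedure is determinate: 15.8 fixes the order, 15.8.2 follows, and the mention of an imputed stop in 15.8.1 is merely redundant. That stands as far as it goes. It does not rescue the result, because the determinate rule is the one that overwrites a recorded stop month. It also leaves wording in 15.8.1 that a second programmer could reasonably apply, with the opposite outcome.

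A second reply is that counting a doubtful medication as concomitant is a cautious convention. That is fair where timing is unknown. Here the recorded month already shows that the drug ended before open-label dosing.

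A third reply is that 15.8.2 is the correct override when the start month is known and the stop month is not. That stands fully (Example 2). Simply letting 15.8.1 win whenever both dates are incomplete would create the mirror error.

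A reader might also infer that the rules distort background antidepressant (ADT) exposure, for instance by giving an ongoing ADT with a year-only start in the dosing year a previous duration of zero. The SAP does not support that as part of this point. An ongoing drug has no stop date, so the two overrides do not meet. Section 7.1 plans to summarise "duration of previous treatment with each qualifying ADT" but does not define where that duration ends. The table of prior ADT in the current episode comes from the questionnaire collected in the lead-in studies (6.0), and ADT compliance comes from its own case report forms (7.2).

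**Conclusion.** The conflict is real and minor. It arises only when both dates are imputed and the imputed start falls after the imputed stop. A change of class further requires a start known only as the year of first open-label dose and a stop with a recorded month before the first-dose month of that year. Every record of that kind moves from prior to concomitant under the stated order.

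A reader might infer that all medications with both dates incomplete are misclassified; the enumeration shows they are not. A reader might also infer a threat to the efficacy results. The relapse definition, the censoring rule and the testing sequence (8.1, 8.2 and 15.3) do not use these imputed medication dates. Only the descriptive prior and concomitant medication summaries are affected. The SAP does not state how many dates are incomplete, so the number of affected records is unknown.

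**What to change.** Replace the two overrides, for records with both dates incomplete and the imputed dates out of order, with one precedence rule that never moves a date outside its recorded month and year:

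- Stop month recorded, start month not: set the imputed start to the imputed stop, as 15.8.1 does.
- Start month recorded, stop month not: set the imputed stop to the imputed start, as 15.8.2 does.

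These two cases cover every clash found in the enumeration. Where one date is complete, the present rules can stay: the complete date is kept and the imputed one moves. The statement on order in 15.8 should be reworded to match, with both dates imputed first and the precedence rule applied afterwards. The cost is a few sentences in the SAP and a small programming change, with no new data.

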#### Missing month and day

[figure not shown]
- If the year of the incomplete stop date is the same as the year of the later of the date of the last dose of open-label IP and the date of last dose of double-blind IP, the month and day of the later of the date of the last dose of open-label IP and the date of last dose of double-blind IP will be assigned to the missing fields.
- If the year of the incomplete stop date is before the year of the later of the date of the last dose of open-label IP and the date of last dose of double-blind IP, *31 Dec* will be assigned to the missing fields.
- If the year of the incomplete stop date is after the year of the later of the date of the last dose of open-label IP and the date of last dose of double-blind IP, *01 Jan* will be assigned to the missing fields.

#### Missing month only

- If only the month is missing, the day will be treated as missing and both the month and the day will be replaced according to the above procedure.

#### Missing day only

- If the month and year of the incomplete stop date are the same as the month and year of the later of the date of the last dose of open-label IP and the date of last dose of double-blind IP, the day of the later of the date of the last dose of open-label IP and the date of last dose of double-blind IP will be assigned to the missing day.
- If either the year of the incomplete stop date is before the year of the later of the date of the last dose of open-label IP and the date of last dose of double-blind IP or if both years are the same but the month of the incomplete stop date is before the month of the date of the later of the date of the last dose of open-label IP and the date of last dose of double-blind IP, the last day of the month will be assigned to the missing day.
- If either the year of the incomplete stop date is after the year of the date of the later of the date of the last dose of open-label IP and the date of last dose of double-blind IP or if both years are the same but the month of the incomplete stop date is after the month of the later of the date of the last dose of open-label IP and the date of last dose of double-blind IP, the first day of the month will be assigned to the missing day.

### **15.10                    ACTUAL TREATMENT FOR ANALYSIS**

If a wrong kit was administered to a patient, the treatment to which a patient was randomized will be used for all the analyses.

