## **2.0 INTRODUCTION**

This Statistical Analysis Plan (SAP) describes the methodology that will be used to summarize the statistical analyses of the efficacy and safety data for the final protocol Amendment 2 of Study RAP-MD-04 (version dated 13 Nov 2018).

Study RAP-MD-04 is a multicenter, double-blind, randomized, placebo-controlled, parallel-group study to evaluate the efficacy, safety, and tolerability of rapastinel as long-term maintenance treatment for patients with major depressive disorder (MDD) who completed 1 of the rapastinel lead-in studies (RAP-MD-01, RAP-MD-02, or RAP-MD-03). While the protocol was written to accommodate the potential recruitment of *de novo* patients, there were no *de novo* patients enrolled. Consequently, all analysis in this document pertains specifically to roll-over patients only.

The study will be conducted for the roll-over patients in the following periods:

- An 8- to 16-week, open-label treatment period (OLTP) where patients receive rapastinel 450 mg IV weekly
- A randomized, double-blind treatment period (DBTP) of at least 26 weeks (and up to 104 weeks) where patients are randomized 1:1:1 to either rapastinel 450 mg weekly, rapastinel 450 mg biweekly or placebo
- A 2-week safety follow-up period (for patients who do not enter the RAP-MD-06 extension study only)

In order for patients to transition from the OLTP and be randomized into the DBTP, the patient must meet the stable responder criterion sometime after 8 weeks (and up to 16 weeks) during the OLTP. A patient will be considered a stable responder upon achieving both criteria (1) and (2) below:

- 1) An observed Montgomery-Asberg Depression Rating Scale (MADRS) total score  $\leq 12$  with no more than one modest MADRS excursion (MADRS total score  $> 12$  but  $\leq 16$ ) for at least 6 consecutive weeks.
- 2) An observed MADRS total score  $\leq 12$  for at least 2 consecutive visits prior to randomization.

To meet these criteria a patient must have no missing MADRS assessments within the last 6 consecutive weeks prior to randomization.

The OLTP starts with the first dose of open-label treatment and ends with 1 of the following: the last scheduled assessment at the Visit 122/Early Termination for patients who do not enter the DBTP; the first dose of double-blind treatment for patients who enter the DBTP.

[figure not shown]

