##### **4.3 DOUBLE-BLIND SAFETY POPULATION**

The Double-blind Safety Population will consist of all patients in the Open-label Safety Population who were randomized to a treatment group during the DBTP of the study and received at least 1 dose of investigational product (IP) during the DBTP.

For by treatment analyses using the Double-blind Safety Population, patients will be assigned to the treatment groups they were randomized to during the DBTP.

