## **8.0 EFFICACY ANALYSES**

All efficacy analyses for the OLTP will be performed using the Open-label ITT Population. All efficacy analyses for the DBTP will be performed using the Double-blind mITT Population. The baseline Day 0 assessment of the lead-in study will be used as the baseline for the OLTP. The Day 0 assessment is the last non-missing assessment before the first dose of Double-blind IP during the placebo lead-in period of their respective lead-in study. The last non-missing assessment before the first dose of Double-blind IP in the DBTP will be used as the baseline for the DBTP. All statistical tests will be 2-sided hypothesis tests performed at the 5% level of significance and all CIs will be 2-sided 95% CIs, unless stated otherwise.

The rater-administered MADRS will be used when deriving endpoints for analyses. The computer-administrated MADRS scores will be provided in a listing.

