An AE (classified by preferred term) that occurs during the SFU of the study will be considered an NEAE if the AE was not present before or at Visit 122 or it was present before or at Visit 122 and increased in severity during the SFU. An AE that becomes serious during the SFU will also be considered as an NEAE. If more than 1 AE is reported before or at Visit 122 and coded to the same preferred term, the AE with the greatest severity will be used as the benchmark for comparison with the AEs occurring during the SFU that were also coded to that preferred term.

An AE that occurs more than 30 days after the date of the last dose of IP will not be counted as an NEAE.

The number and percentage of patients reporting TEAEs and NEAEs during the OLTP will be tabulated overall by SOC and preferred term. The number and percentage of patients in each treatment group reporting TEAEs and NEAEs during the DBTP and during the SFU will be tabulated by SOC and preferred term; by SOC, preferred term, and severity; and by SOC, preferred term, and causal relationship to the IP. If more than 1 AE is coded to the same preferred term for the same patient during the same treatment period, the patient will be counted only once for that preferred term using the most severe and most related occurrence for the summarization by severity and by causal relationship to the IP.

[figure not shown]
The incidence of common ( $\geq 2\%$  of patients in any treatment group) TEAEs and NEAEs during the OLTP will be summarized overall by preferred term. Similarly, the incidence of common TEAEs and NEAEs during the DBTP and during the SFU will be summarized by preferred term and treatment group and will be sorted by decreasing frequency starting with the weekly rapastinel group followed by the biweekly rapastinel group.

[figure not shown]
An SAE that occurred between the date of the first dose of IP in the OLTP and 30 days after the date of the last dose of IP, inclusive, will be considered a treatment-emergent SAE (TESAE). The number and percentage of patients who had TESAEs during the OLTP will be summarized overall by preferred term and sorted by decreasing frequency. The number and percentage of patients who had TESAEs during the DBTP and during the SFU will be summarized by treatment group and preferred term and will be sorted by decreasing frequency starting with the weekly rapastinel group followed by the biweekly rapastinel group.

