**13.0**

**DETERMINATION OF SAMPLE SIZE**

The sample size and power calculations are based on the analysis of time to relapse during the first 52 weeks of the DBTP. Assuming a relapse rate of 19% per 26 weeks in the placebo group and a dropout rate of 20% per 26 weeks in all treatment groups, the sample size of 200 per group will have 90% power to detect a hazard ratio of 0.475 for a rapastinel treatment versus placebo at a 0.05 significance level. To achieve this number of randomized patients, approximately 1500 patients need to be enrolled in this study if 40% of patients are qualified for randomization.

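### Double-blind safety data are analysed as randomised even after wrong kits, which can dilute the rapastinel-placebo safety contrast, probably only slightly

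*SAP*

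**What the plan says.** Section 15.10 is headed Actual Treatment for Analysis, but its rule uses the assigned treatment: "If a wrong kit was administered to a patient, the treatment to which a patient was randomized will be used for all the analyses". It makes no exception for safety. Section 4.3 says the same for by-treatment analyses of the Double-blind Safety Population: "patients will be assigned to the treatment groups they were randomized to during the DBTP". Section 4.4 defines the mITT population as the whole of that safety population, with the same grouping, so the two sets have the same members and the same columns.

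The rule reaches these double-blind outputs:

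- Section 9.1 tabulates "The number and percentage of patients in each treatment group reporting TEAEs and NEAEs during the DBTP and during the SFU". Treatment-emergent SAEs, fatal SAEs and AEs leading to discontinuation are also shown by treatment group.
- Section 7.1 counts infusions by group, and section 7.3 summarises weight-adjusted rapastinel dose by group.

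On the design, section 2.0 says "patients are randomized 1:1:1 to either rapastinel 450 mg weekly, rapastinel 450 mg biweekly or placebo". Section 7.2 sets the expected number of infusions in a period equal to its number of weeks, with no separate rule for the biweekly arm. Section 5.1 counts patients with significant protocol deviations by double-blind group.

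**The concern.** Grouping as randomised protects the efficacy comparison. A safety table answers a different question: what happened to patients who received each treatment. If a placebo patient receives rapastinel kits and then has an AE, these rules report it as a placebo event. If a rapastinel patient receives placebo kits, time without the drug counts as rapastinel experience. When AE risk differs between the two treatments, both errors bring the two columns closer on average. For safety that is the direction that can hide a signal.

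The rule also has no threshold. A patient wrongly treated at most infusions is handled like one with a single slip, and the visible text gives no as-treated view beside the main one.

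**Working it through.** **1. The plan's own design figure.** Section 13.0 states "the sample size of 200 per group will have 90% power to detect a hazard ratio of 0.475", under "Assuming a relapse rate of 19% per 26 weeks in the placebo group and a dropout rate of 20% per 26 weeks". Section 8.0 gives the sidedness: "All statistical tests will be 2-sided hypothesis tests performed at the 5% level of significance". With exponential hazards per week:

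- placebo relapse: −ln(0.81)/26 = 0.00810
- dropout: −ln(0.80)/26 = 0.00858
- rapastinel relapse: 0.475 × 0.00810 = 0.00385

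The chance of an observed relapse by week 52 is λ/(λ+δ) × [1 − exp(−52(λ+δ))], where λ is the relapse hazard and δ the dropout hazard. This gives 0.282 on placebo and 0.147 on rapastinel. Expected events are 200 × (0.282 + 0.147) = 85.8. Freedman's formula gives z = √85.8 × (0.525/1.475) − 1.96 = 1.34, so power is 90.9%. Schoenfeld's formula gives 93.2%. The stated 90% is reproduced. The present point does not depend on it and uses only the 200 per group.

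**2. Dilution.** Let p_P and p_R be the AE risks on placebo and rapastinel, and let m be the share of each of the two arms analysed entirely under the wrong treatment.

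- Observed placebo risk = (1−m)p_P + m·p_R
- Observed rapastinel risk = (1−m)p_R + m·p_P
- Observed difference = (1−2m)(p_R − p_P)

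If only placebo patients are misdosed, the factor is (1−m). The SAP gives neither m nor the AE risks. Taking p_P = 5% and p_R = 10% as assumptions, with a true difference of 5.0 points and a true relative risk of 2.00:

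| m | Patients per arm of 200 | Observed difference (points) | Observed relative risk |
|---|---|---|---|
| 0.5% | 1 | 4.95 | 1.99 |
| 1% | 2 | 4.9 | 1.97 |
| 2% | 4 | 4.8 | 1.94 |
| 5% | 10 | 4.5 | 1.86 |
| 10% | 20 | 4.0 | 1.73 |

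The formula covers swaps between the two arms being compared. Swaps between the weekly and biweekly arms blur those two arms instead.

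**3. Scale of one patient.** One of 200 is 0.5 points, and the 2% cut-off for common events in section 9.1 is 0.02 × 200 = 4 patients. A misdosed patient moves an event's rate by 0.5 points only if that patient has that event.

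**4. Scale of one kit.** At one infusion a week, a single wrong kit is 1/26 = 3.8% of the infusions in 26 weeks and 1/104 = 1.0% of those in 104 weeks. So m is not the share of patients who ever received a wrong kit. It is the much smaller share whose treatment as a whole was another arm's.

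**5. Would a majority rule work?** Section 7.2 expects one infusion a week in every arm. In a double-blind study this implies that biweekly patients alternate rapastinel and placebo kits. That is an inference, as the SAP does not describe the alternation. A correctly dosed biweekly patient with 26 infusions would have 13 of each, a tie. With 27 infusions the split is 14 to 13, and a majority rule would move the patient to weekly or placebo with no kit error at all. Treatment received therefore has to be judged against the planned kit sequence.

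**The case against.** The strongest reply is that the plan is consistent. Sections 4.3, 4.4 and 15.10 state one rule, which keeps the randomised comparison and gives safety and efficacy the same denominators. As-treated safety grouping is a common alternative, but nothing in the visible text promises it. Reassignment is also awkward with repeated dosing: an isolated wrong kit would move nobody, and every randomised patient has already had 8 to 16 weeks of weekly open-label rapastinel, so a stray rapastinel kit is not a first exposure.

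Much of this stands. There is no contradiction between the sections, the effect of isolated errors on AE percentages is slight, and a simple majority rule would do harm in the biweekly arm. But consistency does not make the rule suitable for safety, and the rule also covers the patient treated mainly with the wrong regimen.

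A reader might infer that events after a wrong kit go unflagged. The document does not establish that. Wrong kits may count as significant deviations under a specification not shown. Section 9.1 lists SAEs, deaths and AEs leading to discontinuation, and parts of the safety text are redacted. What can be said is that the deviation counts in section 5.1 do not link an AE to the kit given, and that section 15.10 leaves no room for an as-treated analysis.

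**Conclusion.** The point holds as a minor one. Sections 4.3 and 15.10 fix as-randomised grouping for double-blind safety, and this can attenuate the contrast between rapastinel and placebo. It rests on two conditions: that kit errors occur, and that AE risk differs by treatment. If either fails, there is no expected dilution.

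Under the assumed 5% and 10% risks, 1% of each arm analysed under the wrong treatment turns 5.0 points into 4.9. It takes 5% to reach 4.5. Percentages of common events are therefore unlikely to change much, but one misplaced serious or fatal event could visibly change its table.

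Two stronger readings are not supported. A reader might infer that the safety comparison is biased as it stands, but with no kit-error rate in the SAP only a conditional statement can be made. A reader might also infer that every misdosed patient shifts an arm's AE rate by 0.5 points, but that requires the patient to have the event in question.

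**What to change.** - **Section 15.10:** limit the as-randomised rule to the mITT efficacy analyses.
- **Section 4.3:** for safety, keep each patient in the randomised group unless the kits received over the double-blind period match another arm's planned kit sequence (weekly, biweekly or placebo) better than the randomised arm's. Ties stay as randomised. Do not use a simple majority of infusions. State the matching rule before unblinding.
- **Listing:** show every AE that starts after any wrong kit, with the randomised treatment and the treatment actually given. This covers isolated errors, which reassignment does not touch.

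The cost is SAP wording and use of kit records. No design figure changes. The downside is that safety and efficacy denominators may differ by a few patients, which a footnote can explain.
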